The primary efficacy analysis will be carried out on the ITT population and repeated on the PP population (if different from the ITT population) by Fisher's exact test. Secondary and exploratory efficacy analyses will be analyzed by means of Kaplan-Meier survival estimates and curves and compared between treatment groups by means of the Log-rank test for time to event variables, analysis of covariance (ANCOVA) when adjusting for covariates, or analysis of variance (ANOVA) when without covariates for normally-distributed variables or Wilcoxon rank-sum test for non-normally-distributed variables. Detailed data handling and evaluation procedures and details of the interim review will be described in the Statistical Analysis Plan (SAP).

For the primary endpoint, if the value of the subject is missing, then a conservative imputation rule will be used such that the subject will be treated as having met the condition for the primary efficacy analysis. The choice of analysis method for primary, secondary and exploratory efficacy endpoints will be described in detail in the SAP which will be finalized and signed off before data analysis is performed.

The SAP may include exploratory analyses of various aspects of SMT inclusive of different interventional strategies and evolving treatment modalities. Grifols will analyze the use of COVID-19 specific, potentially disease modifying treatments for any potential differences between study arms. This analysis will be fully detailed in the SAP since medical understanding of COVID-19 interventions is rapidly evolving. For ethical reasons, there are no restrictions placed on what are perceived to be potentially life-saving therapies (apart from participation in another interventional clinical trial).

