**Table 1 Missing Data and Competing Events Coding for Time to Event Data Analyses**

Endpoint	Right Censoring and Competing Events
Time to Clinical Response	Subjects who did not experience clinical response or died at any time during follow-up will be right censored as of the date of last non-missing assessment of NEWS on or prior to Day 29.
Time to Hospital Discharge	Subjects who did not discharge from the hospital at any time during follow-up will be right censored as of the date of last subject contact when the subject was known to be in the hospital. Subject death will be considered a competing event. Competing risk methods e.g., cumulative incidence function (CIF) will be used to account for competing events in the analysis.
Time to Sustained Normalization of Temperature	Subjects who did not meet the criteria for sustained normalization of temperature or died at any time during follow-up will be right censored as of the date of last non-missing assessment of temperature on or prior to Day 29.
Time to Clinical Progression (death, mechanical ventilation, or ICU admission)	Subjects who did not meet the criteria for clinical progression will be right censored as of the date of last subject contact on or prior to Day 29.

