#### 4.6 Data Derivations and Transformations

The following derivations will be used in this study:

Study Day:

- Date of assessment – 1st date of study drug administration + 1 for assessments done on or after the 1st date of study drug administration
- Date of assessment – 1st date of study drug administration for assessments done before the 1st date of study drug administration

Baseline Observation: the last non-missing value prior to the 1st study drug administration.

Duration:

- Duration in days = end date – start date + 1
- Duration in minutes = end time in minutes – start time in minutes

Origin or Start Date for Time to Event Endpoints:

- Time to Clinical Response: date of 1st study drug administration
- Time to Hospital Discharge: date of 1st study drug administration
- Time to Sustained Normalization of Temperature: date of 1st study drug administration
- Time to Clinical Progression: date of 1st study drug administration

Event Date for Time to Clinical Response and time to sustained normalization of temperature:

- If a subject met the criteria for clinical response or sustained normalization of temperature at multiple assessments, the date of the first assessment meeting the definition of clinical response or sustained normalization of temperature will be used as the event date for deriving time to clinical response or sustained normalization of temperature.

Event Date for Time to Clinical Progression

- The event date will be the date of death, the start date of mechanical ventilation, or the date of ICU admission, whichever occurs first.

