### **Time to clinical response**

Clinical response is defined as the NEWS score <=2 maintained for 24 hours from Day 1 through Day 29. The time to the first occurrence of clinical response will be estimated using the Kaplan-Meier (KM) method. The KM estimates along with 95% CI, and survival curves will be provided. Based on the KM estimates, the probabilities of achieving first clinical response and associated 95% CIs on Days 15 and 29 will be reported; in addition, the 25th, 50th (median), and 75th percentiles of the time to first clinical response with associated 95% CIs will be provided, as data permit. The survival rates between treatment groups will be compared using Log-rank test. The p-value from Log-rank test will be presented.

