### **Time to hospital discharge**

Time to hospital discharge is defined as duration of hospitalization from Day 1 through Day 29. The proportion of subjects who are discharged from the hospital will be estimated using the CIF. Deaths that occur prior to discharge from the hospital will be treated as a competing risk. The estimated cumulative incidence and associated two-sided 95% CI on Days 15 and 29 will be displayed. Test for equality of the CIF between treatment groups will be conducted using Gray's test.

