### **Sustained normalization of temperature**

Sustained normalization of temperature is defined as the temperature  $<36.6$  °C armpit (axillary),  $<37.2$  °C oral, or  $<37.8$  °C rectal sustained for at least 24 hours through Day 29.

- The time to the first occurrence of sustained normalization of temperature will be estimated using the KM method. The KM estimates along with 95% CI, and survival curves will be provided. Based on the KM estimates, the probabilities of achieving first sustained normalization of temperature and associated 95% CIs on Days 15 and 29 will be reported; in addition, the 25th 50th (median), and 75th percentiles of the time to first sustained normalization of temperature with associated 95% CIs will be provided, as data permit. The survival rates between treatment groups will be compared using Log-rank test. The p-value from Log-rank test will be presented.
- The proportion of subjects who have experienced sustained normalization of temperature at any timepoint through Day 29 within each treatment group will be presented along with a two-sided exact (Clopper-Pearson) 95% CI.

The observed difference in the proportion of subjects who achieved sustained normalization of temperature at any timepoint between treatment groups along with the exact unconditional 95% CI for risk difference will be calculated. The null hypothesis of no between-treatment difference will be tested using Chi-square statistic and the p-value will be reported.

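### Kaplan-Meier response probabilities run high because deaths are censored; oxygen and ventilator days after death hinge on stop-date entry; ICU days have no rule for deaths never admitted

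*SAP*

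**What the plan says.** **Time to event.** In SAP 4.4, Table 1, subjects who "did not experience clinical response or died at any time during follow-up will be right censored" as of the last NEWS on or before Day 29. The temperature row has the same construction. For hospital discharge the same table says "Subject death will be considered a competing event", and SAP 6.2 repeats it: "Deaths that occur prior to discharge from the hospital will be treated as a competing risk", with a cumulative incidence function and Gray's test.

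SAP 6.2 uses Kaplan-Meier for the other two endpoints. For clinical response, "the probabilities of achieving first clinical response and associated 95% CIs on Days 15 and 29 will be reported". For temperature, "the probabilities of achieving first sustained normalization of temperature and associated 95% CIs on Days 15 and 29 will be reported". Both add percentiles and a log-rank test. For temperature only, a crude figure is also planned: "The proportion of subjects who have experienced sustained normalization of temperature at any timepoint through Day 29".

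On event dates, SAP 4.6 says that if the criteria are met more than once, "the date of the first assessment meeting the definition of clinical response or sustained normalization of temperature will be used as the event date". Protocol 9.1 names Kaplan-Meier estimates, "compared between treatment groups by means of the Log-rank test for time to event variables", and leaves the detailed choice of method for secondary endpoints to the SAP.

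**Durations (SAP 6.2).**
- Hospital days, and ICU days for deaths in the ICU, run on to Day 29 after death without further condition.
- Oxygen and ventilation days run on to Day 29 after an in-hospital death only when the eCRF holds no stop date.
- Subjects never on oxygen or ventilation score zero. For ICU days, the zero rule covers only subjects who are alive.

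**The concern.** A subject who dies before responding can never respond. Censoring that subject lets the later responses of others stand in for the missing one, so one minus Kaplan-Meier (1−KM) is not the probability that SAP 6.2 says it is. The excess grows with deaths before the event, so on these figures it works against an arm that prevents deaths. The SAP avoids this for discharge and gives no reason for treating the other two endpoints differently.

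For oxygen and ventilation, a subject who dies on support gets a value that depends on whether the site closes the record at death. A subject who died in hospital and was never on support has no stop date, and so fits both the carry-forward rule and the zero rule. For ICU days, a death never admitted fits no rule.

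All these endpoints are listed in SAP 8.2 for the futility review. That section sets no numeric rule for them, so the reported figures will be read directly.

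**Working it through.** **Inputs.** From the documents: about 100 subjects randomised 1:1, so about 50 per arm; duration = end date − start date + 1 (SAP 4.6). They state no response or death rates and no figure to reproduce, so all rates below are assumed.

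**1. Size of the excess.** Let r be the true proportion responding by Day 29 and d the proportion dying before response, with constant hazards.
- Total hazard over the period: H = −ln(1 − r − d).
- Response part: H·r/(r + d).
- Day 29: the true value is r, and 1−KM = 1 − exp(−H·r/(r + d)).
- Day 15: scale both hazards by 15/29. The true value is then r/(r + d) × [1 − exp(−H·15/29)].

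With r = 70%:

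| d | H | Response part | 1−KM, Day 29 | Excess (points) | Day 15: 1−KM vs true |
|---|---|---|---|---|---|
| 2% | 1.273 | 1.238 | 71.0% | 1.0 | 47.3% vs 46.9% |
| 5% | 1.386 | 1.294 | 72.6% | 2.6 | 48.8% vs 47.8% |
| 10% | 1.609 | 1.408 | 75.5% | 5.5 | 51.7% vs 49.4% |
| 20% | 2.303 | 1.791 | 83.3% | 13.3 | 60.4% vs 54.1% |

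With d = 5% and r = 50%, 60% or 80%, Day 29 1−KM is 51.6%, 62.1% or 83.2%. With d = 0 the excess is zero.

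**2. Bounds without a hazard assumption.** Take 50 subjects, 35 responders and 5 deaths among the rest. If all deaths precede the responses, 1−KM = 35/(50 − 5) = 77.8%. If all follow the last response, it is 35/50 = 70.0%. With 3 deaths the range is 35/47 = 74.5% down to 70.0%. Only deaths before the event, with later events still to come, cause the excess.

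**3. Between arms.** With a true 70% in both arms, the arm with more deaths looks better by:
- 72.58 − 70.99 = 1.6 points (5% vs 2% deaths)
- 75.54 − 72.58 = 3.0 points (10% vs 5%)
- 75.54 − 70.99 = 4.6 points (10% vs 2%)

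Conversely, give both arms a response hazard of 0.06 per day over 28 days, with deaths before response of 5.2% and 14.4%. True cumulative response is 78.1% and 72.2%, but 1−KM is 1 − exp(−1.68) = 81.4% in both.

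**4. Sampling error at 70%.** One arm: 1.96 × √(0.7 × 0.3/50) = 12.7 points. Difference between arms: 1.96 × √(2 × 0.21/50) = 18.0 points.

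**5. Durations.** For oxygen from Day 1 and death on Day 10, a stop date at death gives 10 − 1 + 1 = 10 days and a blank gives 29, a gap of 19. For death on Day 5 or Day 15 the gap is 24 or 14. Hospital days are 29 either way if the subject was in hospital from Day 1. With 5 versus 2 such deaths per 50, universal entry versus none moves the between-arm mean difference by (5 − 2)/50 × 19 = 1.1 days. With 3 versus 2 deaths it moves by 0.4 days. With equal deaths and equal entry practice it does not move.

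**The case against.** - **The log-rank test.** Censoring deaths is legitimate when the target is the cause-specific hazard. The log-rank test is valid for that and Protocol 9.1 names it. This stands. A reader might infer that the test is wrong and Gray's test must replace it, but that is a choice of estimand and the documents do not require it. The fault lies in what the Kaplan-Meier values are called.
- **Scale.** Even 4.6 points is about a quarter of the between-arm sampling error. The equal-response scenarios also build a higher response hazard into the arm with more deaths. Both remarks stand.
- **Other analyses include death.** It counts in the primary endpoint, the ordinal scale and clinical progression. Conditional power uses the primary endpoint alone, and temperature has its crude proportion. This limits the harm, but clinical response has no crude proportion beside it.
- **The stop-date condition has a purpose.** It counts actual days when support ended before death. The distortion needs stop dates at death to be entered for some subjects and not others, or unequal deaths between arms, and eCRF completion instructions are not among the documents. So the size is conditional; the dependence on one field is not.
- **ICU days.** SAP 2.2.2 words the endpoint as conditional on ICU admission, so a death never admitted might contribute nothing. Yet SAP 6.2 gives zeros to living subjects never admitted, so the planned analysis is not conditional. A reader might infer that such deaths should also score zero. The text does not support that: the zero rule is limited to the living, and SAP 4.4 points to a worst-case approach for selected continuous endpoints, whereas zero is the most favourable score.

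**Conclusion.** The point holds and should be fixed; it does not threaten the trial's main result.

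1. The Day 15 and Day 29 probabilities for clinical response and temperature normalisation are mislabelled and biased upward whenever deaths precede later events. At Day 29 the excess is about 1 to 5.5 points for 2% to 10% deaths before response and about 13 points for 20%, given a true 70% and constant hazards. Actual mortality and timing could make it anything from nil upward.
2. Oxygen and ventilation days for a subject who dies on support depend on stop-date entry, and the carry-forward and zero rules overlap for deaths never on support.
3. A smaller point: ICU days have no stated value for a death never admitted.

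The Table 1 wording might also be read to censor a subject who responded and died later. The first-date rule in SAP 4.6 points the other way, so this is an ambiguity rather than a planned error.

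**What to change.** 1. For both endpoints, report the cumulative incidence function at Days 15 and 29 with death before the event as a competing event, as SAP 6.2 does for discharge. Keep the log-rank test as the cause-specific comparison; Gray's test is optional. Limit the Table 1 wording to deaths before the event, so that a responder who later dies keeps the event at its first date.
2. For oxygen and ventilation days, carry to Day 29 any subject who dies while on support, meaning no stop date or a stop date equal to the date of death. Count actual days when support ended earlier. State that the never-on-support zero rule takes precedence.
3. Before unblinding, state how a death never admitted to the ICU is handled in the ICU-days analysis, consistent with SAP 4.4 and the existing ICU rules, and report the number of such deaths per arm.

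The cost is a few SAP sentences and small programming changes, with no new data. Because Protocol 9.1 leaves these methods to the SAP, an entry in the SAP revision table should be enough. One limit remains: under item 2, a stop date recorded a day before death still scores actual days, so the value continues to rest on accurate dates.

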7.2.5 Day 15±1 day Mandatory for All Subjects

Assessments include the following:

- Ordinal Scale assessment
- NEWS ([Appendix 2](#))
- Clinical features key symptoms: fever, cough, shortness of breath, fatigue, myalgia etc.
- Vital signs (temperature, systolic and diastolic blood pressure, pulse, respiratory rate)
- Record any supplemental oxygen administration (type, %, flow start/end date/time)

GRIFOLS Bioscience Industrial Group			
Number	Version	Status	Effective Date
GC2006-A Multicenter, Randomized, Open-label, Parallel Group Pilot Study to Evaluate the Safety and Efficacy of Prolastin®-C Liquid plus Standard Medical Treatment (SMT) versus SMT alone in Hospitalized Subjects with COVID-19	6.0	Effective	08-Dec-2021
55 of 94			

 If subject requires mechanical ventilation post randomization: Record mechanical ventilation (start/end date/time) Record oxygen saturation (specify on or off oxygen supplementation) Record SAEs and TEAEs Record standard care concomitant medications Respiratory sample for quantitative measurement of SARS-CoV-2 viral load by NAT or PCR (real-time RT-PCR) (obtained via nasopharyngeal swab) Sample for quantitative measurement of IgM and IgG antibodies to SARS-CoV-2 (if antibodies cannot be determined at the site store serum samples frozen at -70°C for later analysis at an external lab) Serum Chemistry (creatinine, albumin, ALT, total bilirubin, LDH) Calculate eGFR using the Cockcroft-Gault formula. Hematology absolute neutrophil & lymphocyte count and standard hematology (hemoglobin, hematocrit, platelet count, leukocyte count with differential) Assessment of ARDS (Berlin Criteria) (Appendix 3) Ferritin, D-dimer, CRP Cytokine panel (IL-1β, IL-10, IL-6, IL-8, IL-2, interferon γ, and TNF-α). Note: serum samples must be stored at -70° C for later analysis at a reference laboratory. Levels of alpha 1-PI (AAT) activity and antigen; both plasma (sodium citrate) and serum samples to be stored at - 70° C for measurement of both antigenic content and functional activity (potency). 			

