7.2.7 Day 29±1 day – All Subjects

Assessments include the following:

GRIFOLS Bioscience Industrial Group	Number	BIG-CL-PRT-000019	Version	6.0	Status	Effective	Effective Date	08-Dec-2021	Page	56 of 94
	GC2006 -A Multicenter, Randomized, Open-label, Parallel Group Pilot Study to Evaluate the Safety and Efficacy of Prolastin®-C Liquid plus Standard Medical Treatment (SMT) versus SMT alone in Hospitalized Subjects with									

 • Ordinal Scale assessment • NEWS (Appendix 2) • Clinical features key symptoms: fever, cough, shortness of breath, fatigue, myalgia etc. • Vital signs (temperature, systolic and diastolic blood pressure, pulse, respiratory rate) • Record any supplemental oxygen administration (type, %, flow start/end date/time) • If subject requires mechanical ventilation post randomization: Record mechanical ventilation (start/end date/time) • Record oxygen saturation (specify on or off oxygen supplementation) • Record hospital discharge date • If subject requires ICU admission post randomization: Record ICU discharge date • Record SAEs and TEAEs • Record standard care concomitant medications • Respiratory sample for quantitative measurement of SARS-CoV-2 viral load by NAT or PCR (real-time RT-PCR) (obtained via nasopharyngeal swab) • Sample for quantitative measurement of IgM and IgG antibodies to SARS-CoV-2 (if antibodies cannot be determined at the site store serum samples frozen at -70°C for later analysis at an external lab) • Serum Chemistry (creatinine, albumin, ALT, total bilirubin, LDH) • Calculate eGFR using the Cockcroft-Gault formula. • Hematology: absolute neutrophil & lymphocyte count and standard hematology (hemoglobin, hematocrit, platelet count, leukocyte count with differential) • Assessment of ARDS (Berlin Criteria) (Appendix 3) • Ferritin, D-dimer, CRP • Cytokine panel (IL-1β, IL-10, IL-6, IL-8, IL-2, interferon γ, and TNF-α). Note: serum samples must be stored at -70° C for later analysis at a reference laboratory. • Levels of alpha 1-PI (AAT) activity and antigen; both plasma (sodium citrate) and serum samples to be stored at - 70° C for measurement of both antigenic content and functional activity (potency). 										

7.2.8 Day 60 \pm 2 days and Day 90 \pm 2 days Phone Checks – All Subjects

- Phone Checks will be performed on Day 60 and Day 90:
- to confirm the subject's vital status (living or deceased)
- to record any hospital re-admissions

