Approximately 100 subjects (who meet the inclusion/exclusion criteria specified in Protocol Sections 5.1 & 5.2) will be randomized in a 1:1 [Liquid Alpha1-PI (Human) plus SMT : Placebo plus SMT] ratio with an interim analysis after 50 subjects (approximately 25 per group). There will be no interruption in study conduct during interim analysis as this simply represents sponsor safety due diligence during the COVID-19 pandemic. An interim futility analysis will be conducted to assess whether the trial will be terminated due to lack of efficacy (futility) based on all available data assessable for the primary endpoint and key secondary efficacy endpoints.

All subjects will be followed daily through Day 10 (note: for Day 6 through Day 10, this stipulation is for as long as subjects are hospitalized). After Day 6, if subjects are discharged from the hospital, evaluations at Day 15 and 29 are required. Subjects remaining hospitalized will be followed daily through Day 29. Phone Checks will occur at Day 60 and Day 90 for vital status (living or deceased), any hospital re-admissions or serious/non-serious AEs after the Day 29 Final Clinic Visit. See Appendix A for the Schedule of Events.

Clinical trial finalization will coincide with the last study visit of the last subject enrolled in the clinical trial. For an individual subject, end of study for the purposes of determining disposition and successful study completion is the Day 29/Final Clinic Visit performed at the scheduled on-study timeframe.

An overview of the study design is presented below:

IV = intravenous; SMT = standard medical treatment

\*Note: If the subject has been discharged from the hospital at the time of the Day 8 blinded Liquid Alpha-1 PI infusion, the 2nd infusion is not mandatory, and is at the discretion of the Principal Investigator and subject

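### Read literally, the SAP Table 1 censoring rule for time to clinical progression can censor discharged, event-free subjects seen on Day 30 back at about Day 15, which biases the Day 29 progression estimate slightly upward

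*SAP*

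**What the plan says.** The relevant provisions are these.

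- **Censoring.** In SAP 4.4, Table 1, subjects without clinical progression are "right censored as of the date of last subject contact on or prior to Day 29".
- **Day count.** SAP 4.6 counts study days, and starts time to clinical progression, from the date of first study drug administration.
- **Visit windows.** Protocol 7.2.7 sets the final visit at "Day 29±1 day – All Subjects", so Day 30 is in window. Protocol 7.2.5 sets the preceding one at "Day 15±1 day Mandatory for All Subjects", that is Days 14 to 16.
- **Contacts after discharge.** SAP 3.1: "After Day 6, if subjects are discharged from the hospital, evaluations at Day 15 and 29 are required". For those still in hospital: "Subjects remaining hospitalized will be followed daily through Day 29".
- **Event dates.** SAP 4.6: "The event date will be the date of death, the start date of mechanical ventilation, or the date of ICU admission, whichever occurs first".
- **Analysis.** SAP 6.2 estimates time to clinical progression by Kaplan-Meier, reports the probability of progression at Days 15 and 29, and compares arms by log-rank test. SAP 8.2 lists this endpoint among those reviewed for futility.

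Neither document says that a contact after Day 29 may be used to carry a subject's event-free time up to Day 29.

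**The concern.** Consider two subjects discharged on Day 10, both seen at about Day 15 and next seen on Day 30. One entered the ICU on Day 22; the other stayed well. The first stays in the risk set until Day 22 and counts as an event. For the second, the Day 30 visit is past the cut-off, so the last usable contact is the Day 15 visit and the subject leaves the risk set there. What decides whether the subject is censored early is the later outcome itself, so the independent-censoring assumption of Kaplan-Meier fails.

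After about Day 15 the risk set loses subjects known to be well, while every late event is kept. If there are such visits and any late events, the Day 29 progression probability can only be pushed upward. At stake are the Day 29 estimate and curve of one secondary endpoint.

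**Working it through.** The plan states no progression rate, discharge rate, visit-timing distribution or power, so there is no figure to reproduce. All rates below are assumptions.

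**Notation.** F = probability of progression by Day 15. q = probability of progression on Days 16 to 29 among those event-free at Day 15. w = share of event-free subjects already discharged by about Day 15 with no other contact on Days 17 to 29. f = share of final visits falling on Day 30.

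**Formulas.**

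- True Day 29 probability: F + (1 − F)q.
- Share of the Day 15 risk set censored back: c = w × f × (1 − q).
- Kaplan-Meier estimate under the literal rule: F + (1 − F)q / (1 − c).

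**Worked arm of 50.** There are 10 events by Day 15, leaving 40 event-free. Two of these progress on Days 16 to 29, and 12 discharged subjects are seen well on Day 30.

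- Full follow-up: 12/50 = 24.0%.
- Literal rule: the risk set falls from 40 to 28, giving 20% + 80% × 2/28 = 25.7%, which is 1.7 points too high.

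**A second set of assumptions.** Take 20% progressing by Day 15 and a further 5% of all subjects later, so q = 0.05/0.80 = 6.25% and the true value is 25%.

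- w = 0.6, f = 0.20: c = 0.6 × 0.20 × 0.9375 = 0.1125, and the estimate is 20% + 5%/0.8875 = 25.6%.
- w = 0.8, f = 1/3: c = 0.8 × 1/3 × 0.9375 = 0.25, and the estimate is 20% + 5%/0.75 = 26.7%.

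**Range of the bias**, with F from 10% to 30% and w from 0.8 to 0.95:

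| f | q | Bias (points) |
|---|---|---|
| 1/3 | 0 | 0 |
| 1/3 | 2% to 5% | +0.5 to +1.9 |
| 1/3 | 10% | +2.2 to +3.6 |
| 10% to 50% | 2% to 10% | +0.1 to +6.7 |

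**Simulation check** (50 per arm, 3000 trials; F = 20%, q = 5%, w = 0.9, f = 1/3; true value 24.0%). The mean Day 29 estimate was 26.0% under the literal rule. It was 24.2% when subjects known to be event-free on or after Day 29 were censored at Day 29. The difference is 1.8 points, with about 11 subjects per arm censored back.

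**Log-rank test.** With no treatment effect and the same discharge and visit timing in both arms, the two-sided type I error in these simulated trials was 0.048 under the literal rule and 0.049 after the fix. With true progression of 30% vs 15% and equal early discharge (70% in both arms, one third of final visits on Day 30), power was 43.6% under the literal rule and 44.1% without the back-censoring. Only with a steep contrast in early discharge (50% vs 80%) was there a visible loss: from 42–44% to 37–40% across separate simulations, and about 1 to 3 points with less late progression.

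**The case against.** **Day 29 may mean the visit.** Both documents also use Day 29 as the name of a visit with a one-day window, and SAP 4.3 summarises data by nominal visit. On that reading a Day 30 visit counts and the problem disappears. This stands as a reason to word the point conditionally. It does not settle the matter: SAP 4.3 concerns summaries, while Table 1 sets a censoring date and SAP 4.6 measures time from the date of first dose.

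**Few subjects may be affected.** This stands. The progression row refers to any contact, so a documented unscheduled contact on Days 17 to 29 moves the censoring date forward. Inpatients are seen daily, and subjects discharged after Day 16 are censored later than Day 16. Protocol 7.2.2 counts days from the Day 1 visit and allows a delayed infusion; for a subject dosed one day late, protocol Day 30 is SAP Day 29 and the visit is kept.

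**It is small.** This also stands. The standard error of a 25% proportion with 50 subjects is √(0.25 × 0.75/50) = 6.1 points, well above the usual bias. But the bias is systematic and costs nothing to remove.

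**Stronger readings that the documents do not support.** A reader might infer that a drug which speeds discharge is materially penalised in the log-rank test. That rests on an assumed, steep discharge contrast which the documents do not supply.

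A reader might also infer that the response and temperature rows need the same change, since the response row is "right censored as of the date of last non-missing assessment of NEWS on or prior to Day 29" and the temperature row is similar. Those events are known only from assessments, so censoring at the last assessment is ordinary practice. Both require the state to hold for 24 hours, which a single Day 30 reading may not show. Capping the time at Day 29 would date a Day 30 finding as Day 29.

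**Conclusion.** The point holds for the time-to-clinical-progression row, on the literal study-day reading. The censoring depends on outcome, and the direction of the bias follows from the rule itself. Its size rests on assumed rates: usually about 0.5 to 2 points on the Day 29 probability, more with many Day 30 visits and late events, and zero if no one progresses after about Day 15 or no final visit falls on study Day 30.

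The log-rank test is little affected unless early discharge differs strongly between arms, and its type I error is not inflated when visit timing is balanced. The primary endpoint is derived from eCRF records under SAP 6.1 and does not use this rule. This is a minor, optional improvement to one secondary analysis.

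**What to change.** Change only the clinical-progression row of Table 1, to read:

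> Subjects without the event who have a visit or contact on or after Day 29 (including an in-window Day 30 visit) confirming event-free status through Day 29 will be censored at Day 29; all others will be censored at their last contact before Day 29.

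This also settles the ambiguity if the nominal visit was what the sponsor meant. Leave the clinical response and temperature normalization rows as they are. The cost is one sentence in the SAP and one line in the derivation. No new data are needed, because death, ICU admission and ventilation dates are already collected.
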